### **9.2 Pharmacodynamic Data**

Absolute PD parameter values will be listed together with changes from baseline and percentage changes from baseline (for CH50 and AP50 percentage of baseline will be listed instead), by study part and study visit.

Absolute values, changes from baseline and percentage changes from baseline will be plotted for the complement parameter C3 by study day with each subject being identifiable. A dotted line will be used to identify follow-up (Part 3). The actual sampling day will be used on the x-axis. The changes and percentage changes from baseline plots will include a reference line for 0 on the y-axis.

For the complement parameters CH50 and AP50 only percentage of baseline values will be plotted by study day with each subject being identifiable. A dotted line will be used to identify follow-up (Part 3). The actual sampling day will be used on the x-axis. A reference line for 100 will be presented on the y-axis.

For the complement parameter C3 values throughout the study will be plotted against time for each subject individually (i.e. one plot per subject). On study transfusions (PRBC only) will be identified on the plot as a vertical line at the relevant study day. Above the profile plot a separate plot will be displayed which shows the APL-2 dose by study day. The study day on both plots will be aligned. For the complement parameters CH50 and AP50 the same plot will be generated using percentage of baseline values instead.

Absolute values in PNH granulocytes (percent FLAER) will be plotted by study day with each subject being identifiable. A dotted line will be used to identify follow-up (Part 3). The actual sampling day will be used on the x-axis. These plots will be repeated for PNH monocytes (percent FLAER).

Individual subject plots of the percentage distribution will be presented for the C3 deposition on RBC cells parameters, with all parameters included on the same subject plot. A dotted line will be used to identify follow-up (Part 3). The actual sampling day will be used on the x-axis. The plot will identify on study transfusions (PRBC only) as a vertical line at the relevant study day; and above the profile plot a separate plot will be displayed which shows the APL-2 dose by study day. The study day on both plots will be aligned. These plots will be repeated for clonal distribution of PNH RBCs parameters.

Clonal distribution of PNH RBCs (percent Type II + III) over time will be plotted with each subject being identifiable. A dotted line will be used to identify follow-up (Part 3). The actual sampling day will be used on the x-axis. These plots will be repeated for Clonal distribution of PNH RBCs (percent Type III), C3d deposition on RBC cells (percent Type II + III) and C3d deposition on RBC cells (percent Type III).

## **10. OTHER ANALYSES**

No other analyses are planned for this study.

## **11. INTERIM ANALYSIS**

Data may be reported while the study is ongoing to help guide decisions to further develop APL-2. These reports will be performed on data that will have been fully checked and considered as final. Any changes to the data previously reported will be fully auditable and discussed in subsequent reports.

## **12. SAFETY MONITORING COMMITTEE**

A periodic safety review will take place on a regular basis by the SMC to review safety/tolerability, PK and PD data. The remit, roles and responsibilities of the SMC is specified in a separate SMC charter.

## **13. DATA HANDLING CONVENTIONS**

### **13.1 General Data Reporting Conventions**

Categorical and count variables will be summarized by the number of subjects (n) and the percent of subjects in each category. Percentages will be displayed with 1 decimal place;

except percentages will not be presented when the count is zero and 100% will be presented as an integer.

Continuous variables will be summarized using the number of observations (n), mean, standard deviation (SD), median, minimum, and maximum. The estimated mean and median for a set of values should be printed out to 1 more decimal place than the original values, and standard deviations should be printed out to 2 more decimal places than the original values. The minimum and maximum should report the same number of decimal places as the original values.

In by-visit summary tables, the baseline will be summarized using all available data, but also for each visit using only the baseline data from subjects with available data at the visit; hence the mean change from baseline will equal the (mean visit value – mean baseline value).

All data will be listed. Data listings will present study days in addition to dates, where study day is derived as (assessment date – first day of dosing+1). The first day of dosing will be identified as Study Day 1. All efficacy, PK and PD listings will present the last dose received prior to the assessment.

### **13.2 Definition of Baseline**

Baseline is defined as the last observed value prior to taking the first dose of investigational product (based on dates or date/times).

### **13.3 Derived Efficacy Endpoints**

#### FACIT-fatigue scale score

The FACIT Fatigue Scale is a 13 item Likert scaled instrument which is self-administered by the subjects during clinic visits. Subject are presented with 13 statements and asked to indicate their responses as it applies to the past 7 days. The 5 possible responses are ‘Not at all’ (0), ‘A little bit’ (1), ‘Somewhat’ (2), ‘Quite a bit’ (3) and ‘Very much’ (4). With 13 statements the total score has a range of 0 to 52. Before calculating the total score, most responses (all except Answers 5 and 7) are reversed to ensure that the higher score corresponds to a higher quality of life.

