10.1.5 Functional Assessment of Chronic Illness Therapy (FACIT) Fatigue Scale

The FACIT Fatigue Scale is a 13 item Likert scaled instrument which is self-administered by the subjects during clinic visits on as outlined in the Study Flow Chart in [Section 2](#). The subject is presented with 13 statements and is asked to indicate their response as it applies to the past 7 days. The 5 possible responses are 'Not at all' (0), 'A little bit' (1), 'Somewhat' (2), 'Quite a bit' (3) and 'Very much' (4). With 13 statements the total score has a range of 0 to 52. Before calculating the total score, some responses are reversed to ensure that the higher score corresponds to a higher quality of life. The FACIT Fatigue Scale and scoring guidelines are provided in the Manual of Procedures (MOP).

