15. APPENDIX 1: FUNCTIONAL ASSESSMENT OF CHRONIC ILLNESS THERAPY (FACIT) FATIGUE SCALE

FACIT Fatigue Scale (Version 4)

Below is a list of statements that other people with your illness have said are important. **Please circle or mark one number per line to indicate your response as it applies to the past 7 days.**

		Not at all	A little bit	Some- what	Quite a bit	Very much
HI7	I feel fatigued	0	1	2	3	4
HI12	I feel weak all over	0	1	2	3	4
An1	I feel listless (“washed out”)	0	1	2	3	4
An2	I feel tired	0	1	2	3	4
An3	I have trouble starting things because I am tired	0	1	2	3	4
An4	I have trouble finishing things because I am tired	0	1	2	3	4
An5	I have energy	0	1	2	3	4
An7	I am able to do my usual activities	0	1	2	3	4
An8	I need to sleep during the day	0	1	2	3	4
An12	I am too tired to eat	0	1	2	3	4
An14	I need help doing my usual activities	0	1	2	3	4
An15	I am frustrated by being too tired to do the things I want to do	0	1	2	3	4
An16	I have to limit my social activity because I am tired	0	1	2	3	4

FACIT-Fatigue Subscale Scoring Guidelines (Version 4)

- Instructions:*
1. Record answers in "item response" column. If missing, mark with an X
 2. Perform reversals as indicated, and sum individual items to obtain a score.
 3. Multiply the sum of the item scores by the number of items in the subscale, then divide by the number of items answered. This produces the subscale score.
 4. **The higher the score, the better the QOL.**

Subscale	Item Code	Reverse item?	Item response	Item Score
FATIGUE SUBSCALE	HI7	4 -	_____	= _____
	HI12	4 -	_____	= _____
	An1	4 -	_____	= _____
	An2	4 -	_____	= _____
	An3	4 -	_____	= _____
	An4	4 -	_____	= _____
	An5	0 +	_____	= _____
	An7	0 +	_____	= _____
	An8	4 -	_____	= _____
	An12	4 -	_____	= _____
	An14	4 -	_____	= _____
	An15	4 -	_____	= _____
	An16	4 -	_____	= _____

Score range: 0-52

Sum individual item scores:	_____
Multiply by 13:	_____
Divide by number of items answered:	_____ (Fatigue Subscale Score)

*For guidelines on handling missing data and scoring options, please refer to the Administration and Scoring Guidelines in the manual or on-line at www.facit.org.

NOTE: The FACIT and all related works are owned and copyrighted by, and the intellectual property of [name]. Permission for use of the FACIT-FATIGUE questionnaire is obtained by contacting [name] at [contact]

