#### **13.5 Handling of Missing, Unused, and Spurious Data**

##### **13.5.1 Missing Data Imputation for Efficacy Endpoints**

No imputation of missing data will be performed.

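### Read by item position, the SAP's FACIT-Fatigue reversal rule scores An3 and An7 backwards; it should name the unreversed items by code

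*SAP*

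**What the plan says.** SAP Section 13.3 (FACIT-fatigue scale score) describes a questionnaire of 13 items, each answered from 0 to 4, and states: "With 13 statements the total score has a range of 0 to 52". On direction of scoring it says that "most responses (all except Answers 5 and 7) are reversed to ensure that the higher score corresponds to a higher quality of life". This is the SAP's only reversal rule. It names no item codes and does not refer to protocol Appendix 1.

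Protocol Section 10.1.5 is less specific. It says that "some responses are reversed to ensure that the higher score corresponds to a higher quality of life", does not say which responses, and points to the Manual of Procedures for scoring.

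Protocol Appendix 1 reproduces the scale and its scoring sheet. The instruction is: "Perform reversals as indicated, and sum individual items to obtain a score". The sheet identifies items by code, not by ordinal number. It marks An5 and An7 to be added as answered (0 +) and the other 11 items to be subtracted from 4 (4 −). For skipped items it adds: "Multiply the sum of the item scores by the number of items in the subscale, then divide by the number of items answered".

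**The concern.** The SAP presents the scale as 13 statements and then excepts answers 5 and 7. A programmer working from that section alone could reasonably count down the questionnaire to the 5th and 7th statements. The codes in Appendix 1 do not match the positions: the list opens with two HI items, and the An numbering skips a value between An5 and An7. Counting therefore lands on a different pair from the one the key leaves unreversed.

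If that happened, two items would pull the total in the wrong direction. The score is listed, summarized by visit and plotted for each subject (SAP Section 6.2.1). With 4 subjects the individual values are in effect the result. The schedule shows one FACIT assessment before dosing, on Day 1, so a mis-scored baseline would enter every change from baseline for that subject.

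**Working it through.** **Inputs.** Item order and scoring key: protocol Appendix 1. Reversal rule and stated range: SAP Section 13.3. Responses run from 0 to 4.

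**Step 1: positions.**

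| Position | Code | Appendix 1 key | SAP rule read by position |
|---|---|---|---|
| 1–4 | HI7, HI12, An1, An2 | reverse | reverse |
| 5 | An3 | reverse | **leave** |
| 6 | An4 | reverse | reverse |
| 7 | An5 | leave | leave |
| 8 | An7 | leave | **reverse** |
| 9–13 | An8, An12, An14, An15, An16 | reverse | reverse |

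The two treatments differ for An3 and An7 only. An5 is scored correctly either way. An3 is worded negatively ("I have trouble starting things because I am tired") and An7 positively ("I am able to do my usual activities").

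**Step 2: reproduce the stated range with the Appendix 1 key.** In the worst state the 11 negative items are answered 4 and An5 and An7 are answered 0: 11 × (4 − 4) + 0 + 0 = 0. In the best state the answers are the opposite: 11 × (4 − 0) + 4 + 4 = 52. This matches the 0 to 52 in the SAP, with higher meaning better.

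**Step 3: the same states with the positional rule.** Worst: An3 contributes 4 instead of 0 and An7 contributes 4 − 0 = 4 instead of 0, so the total is 8. Best: An3 contributes 0 instead of 4 and An7 contributes 4 − 4 = 0 instead of 4, so the total is 52 − 8 = 44. The span from worst to best falls from 52 to 44 − 8 = 36.

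**Step 4: error in one score.** Write x3 and x7 for the responses to An3 and An7.

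Positional − correct = [x3 + (4 − x7)] − [(4 − x3) + x7] = 2 × (x3 − x7).

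With both responses between 0 and 4, the error lies between 2 × (0 − 4) = −8 and 2 × (4 − 0) = +8.

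**Step 5: error in a change from baseline.** It is 2 × (change in x3 − change in x7). As an illustration, let every item improve by one category. Correct change: 13 × 1 = 13. Positional change: 11 items at +1 and two at −1, so 11 − 2 = 9, or 9/13 = 69% of the correct value.

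**Step 6: would a range check find it?** No. Under either key the total is a sum of 13 terms between 0 and 4, so it always lies between 0 and 52.

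**The case against.** The strongest reply is that the phrase is an expansion of the codes. Exactly two items are left unreversed in Appendix 1, and their codes carry the numerals 5 and 7; an author who had counted positions would have written 7 and 8. The SAP sentence also gives its purpose, that a higher score should mean better quality of life, and the positional reading defeats that purpose for An3 and An7. The full key is in the protocol, the SAP says that it elaborates that protocol, and SAP Section 15 declares no change in scoring. How the case report form or dataset labels the items cannot be seen.

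Most of this stands. The code reading is plausible and probably what was meant, and under it the SAP and Appendix 1 agree. What remains is that neither document says An stands for Answer, SAP Section 13.3 does not send the reader to the key, and protocol Section 10.1.5 does not name the items. A correct result depends on the programmer consulting the appendix.

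A reader might also infer two further faults that the documents do not support.

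- *That the error would shrink any real improvement.* By the formula in Step 5 it is zero when An3 and An7 do not change or move by the same amount in the same direction. It inflates the improvement when the An3 response rises relative to An7 while other items improve. The 69% belongs to the uniform example only.
- *That the SAP contradicts the instrument on skipped items, because it omits proration and Section 13.5.1 says* "No imputation of missing data will be performed". The SAP is silent on skipped items within the scale. Appendix 1 already gives the proration as part of scoring, and a bar on imputing missing data does not plainly override it. This is missing detail, not a separate error.

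**Conclusion.** The reversal rule in SAP Section 13.3 is wrong on its literal, positional reading and ambiguous otherwise. On the positional reading An3 and An7 are scored backwards, each total is off by −8 to +8 points, and a uniform one-category improvement shows as 9 points instead of 13. If the phrase stands for the codes An5 and An7, the error is zero.

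A reader might conclude that the FACIT-Fatigue scores are wrong. The documents do not show that: no program or scored data can be seen, and the correct key is in protocol Appendix 1.

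The figures assume that all 13 items are answered and that the questionnaire is presented in Appendix 1 order. The consequence is limited. Enrollment closed at 4 subjects, an abbreviated report is planned, the protocol applies no formal inferential statistics, and this endpoint appears only in listings, descriptive summaries and plots. It still deserves correction, because it is a stated derivation for a secondary endpoint and a mis-keyed score would look plausible.

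**What to change.** Replace the reversal wording in SAP Section 13.3 with: *all items are reversed (4 − response) except items An5 and An7 (the 7th and 8th listed items), per the protocol Appendix 1 scoring key.*

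Then check the scoring program against that key. Two test records are enough to detect this mistake: the worst-state pattern must return 0 and the best-state pattern 52. A program that returns 8 and 44 has used positions.

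The cost is one phrase and a short programming check, with no change to data collection or outputs. SAP Section 1 allows amendments before database lock. After lock, the clarification and the result of the check can be recorded in the clinical study report.

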#### Linear Analog Scale Assessment (LASA)

The Linear Analog Scale assessment (LASA) consists of three items asking respondents to rate their perceived level of functioning. Specific domains include activity level, ability to carry out daily activities, and an item for overall QOL. Their level of functioning is reported

on a 0-100 scale with 0 representing “As low as could be” and 100 representing “As high as could be”. In addition to looking at each domain the combined score (range of 0-300) will be determined.

#### **13.4 Repeated or Unscheduled Assessments of Safety Parameters**

If a subject has repeated assessments before the start of investigational product, then the results from the final assessment made prior to the start of investigational product will be used as baseline. All post-baseline assessments will be used for PCS value determination and all assessments will be presented in the data listings.

#### **13.5 Handling of Missing, Unused, and Spurious Data**

##### **13.5.1 Missing Data Imputation for Efficacy Endpoints**

No imputation of missing data will be performed.

##### **13.5.2 Missing Date of Investigational Product**

When the date of the last dose of investigational product is missing for a subject in the Safety Set, all efforts should be made to obtain the date from the investigator. If it is still missing after all efforts, then the last known date when investigational product was taken will be used in the calculation of treatment duration.

##### **13.5.3 Missing Date Information for Prior or Concomitant Medications (Therapies/Procedures)**

For prior or concomitant medications incomplete (i.e., partially missing) start date and/or stop date will be imputed. When the start date and the stop date are both incomplete for a subject, impute the start date first.

For a missing start date (where stop date is after first dose of investigational product or missing) the date will be imputed as the first dose date of investigational product; for a missing stop date the date will be imputed as the last study date.

The original data will always be presented in the listings.

##### **13.5.3.1 Incomplete Start Date**

The following rules will be applied to impute the missing numerical fields. If the stop date is complete and the imputed start date is after the stop date, then the start date will be imputed using the stop date.

#### 13.5.3.1.1 Missing Day and Month

- If the year of the incomplete start date is the same as the year of the date of the first dose of investigational product, then the day and month of the date of the first dose of investigational product will be assigned to the missing fields
- If the year of the incomplete start date is before the year of the date of the first dose of investigational product, then December 31 will be assigned to the missing fields
- If the year of the incomplete start date is after the year of the date of the first dose of investigational product, then 01 January will be assigned to the missing fields.

#### 13.5.3.1.2 Missing Month Only

- The day will be treated as missing and both month and day will be replaced according to the above procedure.

#### 13.5.3.1.3 Missing Day Only

- If the month and year of the incomplete start date are the same as the month and year of the date of the first dose of investigational product, then the day of the date of the first dose of investigational product will be assigned to the missing day
- If either the year is before the year of the date of the first dose of investigational product or if both years are the same but the month is before the month of the date of the first dose of investigational product, then the last day of the month will be assigned to the missing day
- If either the year is after the year of the date of the first dose of investigational product or if both years are the same but the month is after the month of the date of the first dose of investigational product, then the first day of the month will be assigned to the missing day.

#### 13.5.3.2 Incomplete Stop Date

The following rules will be applied to impute the missing numerical fields. If the date of the last dose of investigational product is missing, then replace it with the last visit date. If the imputed stop date is before the start date (imputed or non-imputed start date), then the imputed stop date will be equal to the start date.

#### 13.5.3.2.1 Missing Day and Month

- If the year of the incomplete stop date is the same as the year as of the date of the last dose of investigational product, then the day and month of the date of the last dose of investigational product will be assigned to the missing fields
- If the year of the incomplete stop date is before the year of the date of the last dose of investigational product, then 31 December will be assigned to the missing fields
- If the year of the incomplete stop date is after the year of the date of the last dose of investigational product, then 01 January will be assigned to the missing fields.

#### 13.5.3.2.2 Missing Month Only

- The day will be treated as missing and both month and day will be replaced according to the above procedure.

#### 13.5.3.2.3 Missing Day Only

- If the month and year of the incomplete stop date are the same as the month and year of the date of the last dose of investigational product, then the day of the date of the last dose of investigational product will be assigned to the missing day
- If either the year is before the year of the date of the last dose of investigational product or if both years are the same but the month is before the month of the date of the last dose of investigational product, then the last day of the month will be assigned to the missing day
- If either the year is after the year of the last dose of investigational product or if both years are the same but the month is after the month of the date of the last dose of investigational product, then the first day of the month will be assigned to the missing day.

#### 13.5.4 Missing Date Information for Adverse Events

For AEs with partial start dates, non-missing date parts will be used to determine if the AE is treatment-emergent or not and for the calculation of study onset day, study stop day and duration. If a determination cannot be made using the non-missing date parts as to when the AE occurred relative to study drug administration, e.g. AE start year and month are the same as the year and month of the first dose of investigational product, then the AE will be classified as treatment-emergent.

To facilitate categorization of AEs as treatment emergent, imputation of dates can be used. For AEs, the default is to only impute incomplete (i.e., partially missing) start dates. Incomplete stop dates may also be imputed when calculation of the duration of an AE is required per the protocol. If imputation of an incomplete stop date is required, and both the start date and the stop date are incomplete for a subject, impute the start date first.

For a missing start date (where stop date is after first dose of investigational product or missing) the date will be imputed as the first dose date of investigational product; for a missing stop date the date will be imputed as the last study date.

The original data will always be presented in the listings.

